1.0 Objectives

1.1 Study Objectives

Aim: To determine the effects of varying both the palatability and portion size of vegetables served to preschool children at a meal on the outcomes of vegetable intake, food intake, energy intake, and energy density at the meal.

Hypotheses:

1. For the outcome of vegetable intake at the meal:
 - a. Enhancing the palatability of vegetables served at the meal will increase vegetable intake.
 - b. Increasing the portion size of vegetables served at the meal will increase vegetable intake.
 - c. Enhancing the palatability of vegetables served at the meal will interact with vegetable portion size to increase its effect on vegetable intake.
2. For the outcome of food intake at the meal:
 - a. Enhancing the palatability of vegetables served at the meal will increase food intake.
 - b. Increasing the portion size of vegetables served at the meal will increase food intake.
3. For the outcome of energy intake at the meal:
 - a. Enhancing the palatability of vegetables served at the meal will increase energy intake.
 - b. Increasing the portion size of vegetables served at the meal will increase energy intake.
 - c. Enhancing the palatability of vegetables served at the meal will interact with vegetable portion size to increase its effect on energy intake.
4. For the outcome of food energy density at the meal:
 - a. Enhancing the palatability of vegetables served at the meal will increase energy density.
 - b. Increasing the portion size of vegetables served at the meal will decrease energy density.

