6.0 Study Design and Procedures

6.1 Study Design

This study will have a within-subject design with four experimental conditions. Once a week for four weeks, children will be served a meal consisting of a main dish, fruit, vegetables, and milk. On different occasions, the vegetables served at the meal will be varied in both palatability and portion size. The palatability will be either standard (steamed, plain vegetables) or enhanced (vegetables with added flavoring) and the portion size will be either baseline (100%) or larger (200% of baseline).

The experimental conditions will be as follows:

1. Standard palatability of vegetables and 100% portion size of vegetables
2. Standard palatability of vegetables and 200% portion size of vegetables
3. Enhanced palatability of vegetables and 100% portion size of vegetables
4. Enhanced palatability of vegetables and 200% portion size of vegetables

The order of presenting the conditions across study weeks will be counterbalanced by classroom. All meals will meet the minimum guidelines outlined by the USDA and Child and Adult Care Food Program (CACFP).

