7.2 Sample size determination

A power analysis was performed to determine the sample size needed to detect the effect on vegetable intake of enhancing the vegetables with small amounts of salt and butter; this effect was considered to be more difficult to detect than that of portion size. The variability in vegetable intake was estimated from a study in which toddlers were served vegetables with different amounts of butter and salt at different lunches (Bouhlal et al., 2011), as well as from our previous studies in 3- to 5-year-old children (Smethers et al., 2019; Sanchez et al., 2019). The difference in vegetable intake to be detected was set at 10 g, which is about one-third of the minimum vegetable serving size of the Child and Adult Care Food Program (CACFP) for lunch in this age group. In order to detect this difference in vegetable intake, the required sample size was estimated to be 49 children using a Type 1 error rate of 5% and a power of 80%. In order to allow for absences and withdrawals, we will aim to enroll at least 65 children in the study.

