7.3 Statistical methods

The primary outcome of this crossover study will be children's vegetable intake by weight. Secondary outcomes will be meal food and milk intake, meal energy intake, and the energy density of the food consumed at the meal. Differences in mean outcomes across the two experimental factors will be analyzed using linear mixed models with repeated measures. The fixed factors in the model will be the experimental conditions of portion size (100% or 200%) and flavor (plain or enhanced), as well as study week, classroom, and sex of the child. The interaction between the factors of portion size and flavor will be tested for significance in all models and removed if not significant. Participants will be treated as a random effect. The Tukey-Kramer method will be used to adjust the significance level for multiple pairwise comparisons between means. Children who left <7 g of vegetables uneaten at ≥ 3 meals will be identified as "plate cleaners", and vegetable intake will be analyzed both with and without these children.

Analysis of covariance with linear mixed models will be used to assess the influence of continuous participant characteristics (age, body weight, height, BMI-for-age percentile, BMI z-score, questionnaire subscales) on the relationship between experimental factors and vegetable intake. Categorical subject characteristics (sex, preference ratings for both versions of vegetables, and liking and ranking ratings of all meal components) will be tested as factors in the models. Ordinal logistic regression will be used to evaluate whether the distribution of the liking ratings of the vegetables differed significantly between the plain and enhanced versions; results will be reported as odds ratios with 95% confidence levels. Differences between boys and girls in age, body weight, height, BMI-for-age percentile, and BMI z-score will be evaluated by using t-tests. Outcomes from statistical models will be considered significant at $p < 0.05$. All data will be analyzed with SAS software (SAS 9.4, SAS Institute, Inc.).

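### Butter in the enhanced recipe adds energy at equal intake, so hypotheses 3a, 4a and (if larger portions raise vegetable grams) 3c do not isolate palatability

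*Combined protocol and SAP*

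**What the plan says.** Section 1.1 states three energy predictions for palatability:

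- 3a: "Enhancing the palatability of vegetables served at the meal will increase energy intake".
- 3c: palatability "will interact with vegetable portion size to increase its effect on energy intake".
- 4a: "Enhancing the palatability of vegetables served at the meal will increase energy density".

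Hypothesis 1b predicts that larger portions raise vegetable intake. Hypothesis 4b predicts that larger portions lower energy density.

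Section 6.1 describes the enhanced condition only as vegetables with flavoring added, set against plain steamed ones. The ingredients appear in section 7.2, which refers to "enhancing the vegetables with small amounts of salt and butter". No amount and no kcal per gram is given for either version.

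Section 7.3 says: "Secondary outcomes will be meal food and milk intake, meal energy intake, and the energy density of the food consumed at the meal". Each outcome is analyzed with a mixed model that has one plain/enhanced flavor factor, a portion factor and their interaction, which is dropped if not significant. The documents describe no energy-matched recipe, no calculation that separates the butter's energy, and no caveat on this point.

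**The concern.** Flavor in this trial changes two things at once: how much the child may like the vegetables, and how many kcal each gram contains. The gram outcomes respond to the first. The kcal and kcal/g outcomes respond to both, and the hypotheses credit the whole difference to palatability.

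A positive 3a or 3c could therefore be read as children eating more energy because the food tasted better, when part or all of the difference comes from the butter in the dish. For 4a the two routes oppose each other. With other intake unchanged, eating more of a low-energy vegetable lowers meal energy density, which fits the direction of 4b, while butter raises it. The observed sign can then differ from the sign of the eating response. Section 2.3 presents the study as one about palatability and section 10.2 points to obesity prevention, so readers are likely to interpret the energy results as behavior.

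**Working it through.** **Plan's own figure.** There is none for energy. The only calculation (section 7.2: 49 children, 10 g, 5% error rate, 80% power) concerns vegetable grams. Its SD is not stated, so it cannot be reproduced and says nothing about the energy outcomes.

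**Assumptions (not in the documents).** Plain vegetables p = 0.3 or 0.5 kcal/g. Butter 7.2 kcal/g at share b = 3%, 5% or 10% of dish weight. Other food 220 g at 1.5 kcal/g = 330 kcal. Vegetable intake 30 g at the 100% portion and 45 g at 200%, the same for both flavors. Flavor therefore has no effect on eating; portion size adds 15 g.

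**Formulas.**

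- Recipe difference d = b × (7.2 − p).
- 3a, recipe only = mean vegetable grams × d = 37.5 × d.
- 3c, recipe only = portion effect in grams × d = 15 × d.
- 4a, recipe only, at 30 g = 30 × d / (220 + 30).

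| b | p | d (kcal/g) | 3a (kcal) | 3c (kcal) | 4a (kcal/g) |
|---|---|---|---|---|---|
| 3% | 0.3 | 0.207 | +7.8 | +3.1 | +0.025 |
| 3% | 0.5 | 0.201 | +7.5 | +3.0 | +0.024 |
| 5% | 0.3 | 0.345 | +12.9 | +5.2 | +0.041 |
| 5% | 0.5 | 0.335 | +12.6 | +5.0 | +0.040 |
| 10% | 0.3 | 0.690 | +25.9 | +10.4 | +0.083 |
| 10% | 0.5 | 0.670 | +25.1 | +10.1 | +0.080 |

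**Condition on 3c.** If intake is 30 g in all four cells, the butter adds 30 × d at both portion sizes. The interaction is 30d − 30d = 0 for any recipe. It is a recipe artifact only when the portion effect on grams is not zero.

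**Wider range.** With p from 0.3 to 0.6, 15-60 g of vegetables and 200-300 g of food in total:

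- 3a runs from 0.198 × 15 = +3 kcal to 0.690 × 60 = +41 kcal.
- 4a runs from 0.198 × 15 / 300 = +0.01 to 0.690 × 60 / 200 = +0.21 kcal/g.
- 3c, for a portion effect of 5-30 g at p = 0.45, runs from 0.03 × 6.75 × 5 = +1 kcal to 0.10 × 6.75 × 30 = +20 kcal.

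**Sign of 4a.** Suppose enhancement adds the 10 g of section 7.2 (30 g to 40 g), with other intake fixed. The comparison is with the plain meal at 30 g.

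| p | Plain, 30 g | 40 g at plain kcal/g | 40 g, 3% butter | 40 g, 5% butter |
|---|---|---|---|---|
| 0.3 | 339/250 = 1.356 | 342/260 = 1.315 | 350.28/260 = 1.347 | 355.8/260 = 1.368 |
| 0.5 | 345/250 = 1.380 | 350/260 = 1.346 | 358.04/260 = 1.377 | 363.4/260 = 1.398 |

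Eating alone lowers energy density in both rows. At 3% butter the observed value still falls; at 5% it rises. Break-even needs an enhanced value of (1.356 × 260 − 330)/40 = 0.564 kcal/g when p = 0.3, so b = 0.264/6.9 = 3.8%. When p = 0.5 it needs (1.380 × 260 − 330)/40 = 0.720 kcal/g, so b = 0.220/6.7 = 3.3%.

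**The case against.** The hypotheses do not say that energy rises because children eat more. Sections 6.1 and 7.3 define the factor by what is served, plain or enhanced, and the total energy effect of the enhanced dish is a legitimate estimand. Hypothesis 4a makes most sense on that reading: since 4b expects more vegetables to lower energy density, a predicted rise under enhancement already implies the added energy. This stands. It supports keeping the observed totals as the planned outcomes and changing what they are attributed to.

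Section 7.3 also tests vegetable grams (the primary outcome) and food and milk intake with the same flavor factor. If eating did not change, those results would be reported beside the energy results. This also stands, so a reader should not infer that the energy hypotheses are unanswerable or that intake goes unexamined. But the gram results do not give the size of the recipe's share in the energy effect, or say whether an energy interaction is more than a portion effect multiplied by d.

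Nor is confirmation guaranteed. Less main dish eaten could offset the butter's energy, and the plan requires p < 0.05. With no SD for energy or energy density and no stated butter amount, the chance of significance cannot be computed.

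Liking and preference ratings are collected, but section 7.3 uses them as factors for vegetable intake. They do not separate recipe energy from eating.

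**Conclusion.** The concern holds as a point about attribution. At equal grams of every food, 3a and 4a rise by arithmetic for any vegetable intake above zero. Under the assumptions in the first table, the recipe alone gives about +7.5 to +26 kcal per meal for 3a and +0.02 to +0.08 kcal/g for 4a. For 3c it gives about +3 to +10 kcal, given a 15 g portion effect common to both flavors. The direction follows from the added butter. The sizes rest wholly on assumed recipe and intake values.

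Three stronger readings are not supported:

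- That 3c rises even if no child eats differently. Without a portion effect on grams it is exactly zero.
- That the sign of 4a will be reversed. In the example this needs roughly 3.3-3.8% butter or more, and the documents state only that the amounts are small.
- That the main result is compromised. The primary endpoint and the sample size are in grams and are not affected by this kcal mechanism.

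This is a worthwhile, inexpensive improvement to secondary outcomes.

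**What to change.** 1. State the kcal per gram of the plain and enhanced vegetables in the protocol.
2. Keep observed energy intake and energy density as the planned secondary outcomes, but word 3a, 3c and 4a as effects of serving the enhanced (butter and salt) recipe.
3. In section 7.3, add a supportive analysis with the same mixed model in which vegetable grams eaten in the enhanced conditions are valued at the plain-vegetable kcal/g. Report the difference between the observed and supportive estimates as the recipe contribution.
4. Claim a behavioral energy effect, or a behavioral interaction of portion size with flavor on energy, only if the supportive analysis shows it, read together with the gram outcomes.

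The cost is wording plus one derived variable per outcome. All items are already weighed and energy values are needed anyway; no procedure, sample size or primary analysis changes. The price is more cautious claims.

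One limit should be stated in the plan: the supportive analysis does not remove any effect that the butter's energy has on how much of the other foods children eat. It is therefore an aid to interpretation and should not replace the observed outcomes as the basis for the planned tests.

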1.2 Primary Study Endpoints

1. Weight (grams) of vegetables consumed at the meal

1.3 Secondary Study Endpoints

1. Weight (grams) of food consumed at the meal
2. Energy (kilocalories) consumed at the meal
3. Energy density (kilocalories/gram) of food consumed at the meal

2.0 Background

2.1 Scientific Background and Gaps

The US Dietary Guidelines recommend that 3- to 5-year-old children consume at least one to two servings of vegetables each day (USDA, 2015). The majority of children, however, do not meet these recommendations (Ramsay et al., 2014). This finding has been attributed in part to children's low preference for vegetables compared to other foods (Ishdorj et al., 2015; Nicklaus et al., 2004). As a strategy to increase vegetable intake in children, a number of studies have tested serving larger portions of vegetables at a meal (Mathias et al., 2012; Spill et al., 2010; Kral et al., 2010). The results of these portion size studies, however, have been variable, which might be explained by differences in the palatability of the vegetables that were tested in the studies. It remains to be investigated whether increasing the palatability of vegetables compared to other meal components promotes vegetable intake when larger portions are served. Thus, this experiment aims to assess whether the palatability of vegetables influences vegetable intake in response to increases in vegetable portion size at a meal.

2.2 Previous Data

In a previous study in preschool children (Matthias et al., 2012), the portion size of vegetable side dishes served at a meal was doubled, and it was found that this led to an overall increase in vegetable intake. However, a significant increase was only observed in the children who reported liking the vegetables (57% of children). These findings show that increasing the portion size of vegetables can lead to increases in intake in preschool children, but suggests that the effect depends on the palatability of the vegetables.

2.3 Study Rationale

This study will increase understanding of the effects of vegetable palatability on children's vegetable intake and will assess whether increases in palatability can be used in conjunction with increased portion size to promote vegetable intake in preschool children.

3.0 Inclusion and Exclusion Criteria

3.1 Inclusion Criteria

1. Children who are between the ages of 3 and 5 years old and who are enrolled in a scheduled classroom of the childcare center.

3.2 Exclusion Criteria

1. Children who are allergic to any of the foods served
2. Children whose diets exclude any of the foods served

3. Children who will not be present at the childcare center for all of the scheduled study days (due to scheduled vacations, part-time enrollment at the childcare center, etc.).

3.3 Early Withdrawal of Subjects

3.3.1 Criteria for removal from study

Subjects will be removed from the study if they repeatedly fail to follow study protocol.

All participation is voluntary. Children can refuse to participate in any session and parents, children, and teachers may withdraw from the study at any time.

3.3.2 Follow-up for withdrawn subjects

N/A

4.0 Recruitment Methods

4.1 Identification of subjects

Children who are enrolled in the scheduled classroom at the childcare center, along with their parents or guardians, will be invited to participate.

Teachers in the classrooms of participating children will be invited to participate.

4.2 Recruitment process

4.2.1 How potential subjects will be recruited

We will recruit using a parent letter placed in each child's mailbox at the childcare center. A trained staff member who is approved to do recruitment and consenting of subjects will be available in the center during child pick up or drop off to explain the study and answer any questions parents may have.

Teachers in classrooms of participating children will be verbally invited to participate by study staff.

4.2.2 Where potential subjects will be recruited

At the childcare center.

4.2.3 When potential subjects will be recruited

We will work with local child care centers to identify times which we can come in to collect data. 2 – 4 weeks before data collection begins, we will recruit participants.

4.2.4 Describe the eligibility screening process and indicate whether the screening process will occur before or after obtaining informed consent

Children with allergies to foods served, or whose diets exclude these foods, will not be eligible to participate in this study. Children with > 1 previously planned absence during any of the study days will also be excluded from participation.

A screening questionnaire regarding food allergies, dietary exclusions, food intolerances, and attendance during planned study days will be included with the consent form.

5.0 Consent Process and Documentation

5.1 Consent Process:
Check all applicable boxes below:

- Informed consent will be sought and documented with a written consent form [Complete Sections 5.2 and 5.6]**
- Implied or verbal consent will be obtained – subjects will not sign a consent form (waiver of written documentation of consent) [Complete Sections 5.2, 5.3 and 5.6]**
- Informed consent will be sought but some of the elements of informed consent will be omitted or altered (e.g., deception). [Complete section 5.2, 5.4 and 5.6]**
- Informed consent will not be obtained – request to completely waive the informed consent requirement. [Complete Section 5.5]**

5.2 Obtaining Informed Consent

5.2.1 Timing and Location of Consent

The consent form will be signed by the parent prior to their child's enrollment in the study. Consent will be obtained at the childcare center with a trained member of the lab staff present.

Teachers will consent (to fill out questionnaires about enrolled children) at the childcare center during the first study week in their classroom.

5.2.2 Coercion or Undue Influence during Consent

Parents will be given the consent form to take home to review on their own and can decide whether they want their child to participate.

Teachers will be given the opportunity to review the consent form on their own and can decide if they wish to participate.

5.3 Consent – Other Considerations

5.3.1 Non-English-Speaking Subjects

It is not anticipated that there will be any non-English speaking or illiterate parent participants.

5.3.2 Cognitively Impaired Adults

5.6.2.1 Capability of Providing Consent

N/A

5.6.2.2 Adults Unable to Consent

N/A

5.6.2.3 Assent of Adults Unable to Consent

N/A

5.3.3 Subjects who are not yet adults (infants, children, teenagers)

5.6.3.1 Parental Permission

Parents will sign consent for their child to participate. Two copies of the consent form will be provided, one to be signed and returned to study staff, and one to be kept for parents' records.

5.6.3.2 Assent of subjects who are not yet adults

Children can refuse to eat any meal if they choose. Before beginning measurement of height and weight or the Tasting Game, children will be asked if they want to participate and can refuse to do so.

6.0 Study Design and Procedures

6.1 Study Design

This study will have a within-subject design with four experimental conditions. Once a week for four weeks, children will be served a meal consisting of a main dish, fruit, vegetables, and milk. On different occasions, the vegetables served at the meal will be varied in both palatability and portion size. The palatability will be either standard (steamed, plain vegetables) or enhanced (vegetables with added flavoring) and the portion size will be either baseline (100%) or larger (200% of baseline).

The experimental conditions will be as follows:

1. Standard palatability of vegetables and 100% portion size of vegetables
2. Standard palatability of vegetables and 200% portion size of vegetables
3. Enhanced palatability of vegetables and 100% portion size of vegetables
4. Enhanced palatability of vegetables and 200% portion size of vegetables

The order of presenting the conditions across study weeks will be counterbalanced by classroom. All meals will meet the minimum guidelines outlined by the USDA and Child and Adult Care Food Program (CACFP).

6.2 Study Procedures

1. On one day a week for four weeks, enrolled children will be served a lunch of foods commonly served in the childcare center and following the regular meal schedule. Menus have been developed from the childcare center menus to be as similar as possible to the foods that children are served regularly. Milk will be served as beverage. Meals will be served at tables of 3 to 6 children and one adult, which is a standard practice at the childcare centers. The adults at the table will be instructed not to discuss the food or to encourage the children to eat. Each participant will be served an individual pre-weighed meal. All food and beverage items will be weighed with an electronic food scale before and after meals in order to determine the amount consumed. Participants will be told they can eat as much or as little of the foods as they would like. Trained research personnel will observe each mealtime and will document food and beverage spillage and any comments made about the food.

2. After all study meals are completed, trained research personnel will return to the childcare center to measure the height and weight of enrolled children. Body weight will be measured in triplicate using a portable digital scale. Height will be measured in triplicate using a portable stadiometer. Enrolled children will also be invited to participate in the Tasting Game. They will be asked to taste a small amount of each food served in the study and indicate their liking of the food by pointing to one of three cartoon faces (Yummy, Just OK, and Yucky). Children will also be asked to rank their liking of each food in the meal and to indicate their preference for the vegetables with enhanced palatability compared to those with standard palatability.

3. Parents will be asked to complete a demographic questionnaire, the Children and Adult Eating Behavior Questionnaire, the Vegetable Questionnaire, and a portion of the Child Feeding Questionnaire. These questionnaires (4 total) will assess whether certain child eating behaviors or parental feeding behaviors influence food intake. All will be administered and completed via paper and pencil.

4. Photographs may be taken in the childcare center of children eating meals, participating in the Tasting Game, and having their height and weight measured. Taking such photographs will be subject to the consent provided by each parent concerning their child.

5. For each enrolled child, the classroom teacher who is most familiar with the child's eating behavior will complete one questionnaire (Children's Eating Behaviour Questionnaire). All will be administered and completed via paper and pencil.

6.2.1 Visit 1

Enrolled children will be served a lunch of foods commonly served in the childcare center and following the regular meal schedule. Milk will be served as beverage. Meal 1 will be served at tables of 3 to 6 children and one adult, which is a standard practice at the childcare centers.

Each participant will be served an individual pre-weighed meal. All food and beverage items will be weighed with an electronic food scale before and after meals in order to determine the amount consumed. Participants will be told they can eat as much or as little of the foods as they would like. Trained research personnel will observe each mealtime and will document food and beverage spillage and any comments made about the food.

